Orthodontic treatment is adopted by wide section of society not only for the corrections of malocclusion but also improves mastication, speech and appearance, as well as overall health, comfort, and self-esteem (**Westley, 2010**). There are two types of orthodontic appliances either removable or fixed appliance. Although the orthodontic appliance has many known benefits, these appliances are also associated with a number of damages and disorders of oral cavity (**Pathak and Sharma, 2013**). Polymethyl methacrylate (PMMA) is the standard material for denture bases because of its biocompatibility, low cost, ease of processing, high flexural resistance and flexural modulus, and low water solubility (**Leão *et al.*, 2018**); however, the PMMA denture base is susceptible to microbial colonization in the oral environment (**Puri *et al.*, 2008**) other factors that favor microbial colonization are porosity, surface roughness, poor denture hygiene, and continual and nighttime wearing of dentures (**Gendreau and Loewy, 2011**). Rougher surfaces have been found to be more difficult to clean and promote re-growth by surviving organisms as opposed to complete surface re-colonization (**Teughels *et al.*, 2006**).

Physiologically the human's oral microflora consists of a mixture of organisms, which are common also to other anatomical districts. This bacterial charge is extremely complex, being composed of over 700 different

species of bacteria (**Relman, 2015**). Biofilm is a matrix-enclosed microbial accretion that adheres to biological or non-biological surfaces (**Hall-Stoodley et al., 2004**). Bacterial biofilms are a serious global health concern due to their abilities to tolerate antibiotics, host defense systems and other external stresses; therefore it contributes to persistent chronic infections (**De la Fuente-Núñez et al., 2013**). Formation of biofilm is a well-regulated multi-step event such as (i) adsorption of molecules (macro and micro molecules) to surfaces; (ii) bacterial adhesion to the surface and release of extracellular polymeric substances (EPS); (iii) colony formation and biofilm maturation. (**Flemming et al., 2007**). Patients need to be aware of the implications for their oral health when undergoing recommended orthodontic treatment. On the other hand, when a patient accepts to undergo orthodontic treatment, including those using removable orthodontic devices, he/she should be reminded that it entails a commitment to a higher regimen of attention towards oral hygiene and health in patient's home care (**Al Makhmari et al., 2017**). Recently, **Rodríguez-Rentería et al. (2021)** investigated after 4 weeks the frequency of *Staphylococcus aureus*, *Pseudomonas aeruginosa*, and *Candida* species on removable orthodontic appliances and found that, of the 55 removable orthodontic appliances studied, *Staphylococcus aureus* was present on 90.9%, *Pseudomonas aeruginosa* on 67.7% and *Candida* species on 32.7% of the appliances. Interestingly, these microorganisms were also found in the support oral mucosa of the 55 children (89.09%; 60%; 30.9% respectively). The authors also concluded a direct relationship between removable orthodontic treatment and an increase in the amount of periodontal pathogenic microorganisms. Surface roughness, incomplete polymerization, or wear caused by daily brushing of the appliance seems to directly influence bacterial and fungal biofilm adhesion to removable acrylic appliances.

The denture base after processing is finished using acrylic finishing bur and sandpaper and polished using a rag wheel and cone with pumice slurry. The surface roughness of the denture base material has a substantial effect on plaque adherence and microbial colonization of the prostheses. A rough surface creates niches in which microorganisms are protected against mechanical dislodging forces. The bacteria can subsequently spread over the denture surface from these niches. It has been proven that an increase in surface roughness above a threshold of 0.2 μm results in a simultaneous increase in plaque accumulation. This concept is of clinical importance because patients need to have a smooth surface to deter the formation of a biofilm. This is an esthetic concern as well as an overall concern for maintaining good oral hygiene. **Bollen et al. (2017)** found that the surface roughness of acrylic resin can be dependent on the polishing grit. *Streptococcus sanguis*, *Bacteriodes gingivalis*, and *Candida albicans* adhere in very high numbers to roughened acrylic resin versus smooth acrylic resin. **Al Groosh et al. (2015)** investigated the influence of surface roughness and surface dynamics on the attachment of Methicillin-Resistant *Staphylococcus aureus* (MRSA) onto orthodontic retainer materials and found that the number of bacteria attached to the surface of the tested materials increased over the 48 h time period regardless of the material chemistry and surface topography. There was no significant difference in MRSA biofilm formed on the surface of these materials. However, the scanning electron microscope and the Confocal laser scanning microscopy showed that the distribution of bacterial aggregates increased on the rougher surface of the auto polymerized acrylic samples whereas the pattern of bacterial attachment was more uniformly distributed on the thermoplastic samples.

Some studies have already been conducted in order to investigate the effects of different cleaning protocols for acrylic removable orthodontic appliances and may also help to reduce the risk of oral diseases related to biofilm growth, some different processes have been described such as denture cleaners, enzymatic solutions, chlorhexidine, sodium hypochlorite, or homemade solutions containing vinegar or citric acid (**Eichenauer *et al.*, 2011**). The two major approaches used for denture cleaning are mechanical and chemical methods. Mechanical methods include brushing (using water, soap, toothpaste, or abrasives) and ultrasonic treatment. Mechanical cleaning with brushes is inexpensive and common, but elderly and disabled patients might face difficulties with this method because of poor motor coordination, poor dexterity, and low motivation. There is evidence that mechanical cleaning with toothpastes can result in significant wear of conventional acrylic resins. Chemical method includes immersion of dentures in different cleansing solutions. Immersion in cleansing solution is an inexpensive, easy, and comfortable alternative procedure. Moreover, the cleansing solution can reach undercuts of the denture base that are difficult to clean mechanically, resulting in more efficient cleaning (**Schwindling *et al.*, 2014**).

No study is conducted to evaluate the most effective method used to remove biofilm from removable orthodontic appliance.

Research question:

What is the most effective method of cleaning an acrylic based removable orthodontic appliance?

Research hypothesis

The null hypothesis: There is no difference between the different methods of cleaning acrylic based removable orthodontic appliances.

Aims of the study:

The aims of the current study are:

1. To evaluate the effects of different cleaning regimes i.e. chemical and mechanical on biofilm formation of an acrylic based removable orthodontic appliance.
2. To find out if surface modification i.e. polished acrylic fitting surface, have an impact on cleaning the biofilm formation.

Methodology

Study design:

An in vivo study.

Setting:

It is double-blind, parallel, randomized clinical trial conducted in the orthodontic clinic after obtaining the ethical approval from the ethics committee of the department.

Subjects:

Orthodontic patient will be selected to wear a removable appliance for the study period.

Sample size:

Thirteen orthodontic patients for each group will be selected to wear a removable orthodontic appliance for the study period (**Lima et al., 2006**) and will be instructed for the cleaning protocol according to the manufacturer's instructions.

Inclusion criteria:

- Presence of full upper permanent dentition;
- Well-aligned teeth or mild crowding (less than 3mm);

- No history of sensitivity to any ingredient contained in the cleaning materials;
- Nonsmoker;
- Caries free.

Exclusion criteria:

- Participant taking steroid-based or antibacterial mouthwash or broad-spectrum antibiotics;
- Mouth breather;
- Participant taking medication that reduces salivary flow;
- Pregnant or lactating female (**Albanna *et al.*, 2017**).

All of the study steps were explained to the participants verbally and in writing, written informed consent will be obtained from each participant.

Materials and instruments**Materials used for orthodontic removable appliance fabrication:**

- Acrylic powder and monomer (Orthocryl, Dentaaurum, Ispringen, Germany).
- 0.7 mm stainless steel wire (Spring hard, Dentarum, Ispringrn, Germany).
- Adam's plier.
- Sticky wax.
- Separating medium.
- Cutter.
- Wax knife.
- Mold material.

Materials used for cleaning regimes:

- 1-Brush (dental or denture brush) with chlorhexidine (CHX) toothpaste.
- 2-Chemical cleaning i.e. Lacalut cleaning tablet.
- 3-Combination of brushing with CHX toothpaste and cleaning tablet.

Materials and equipment used form microbial isolation and identification:

1. Calcium alginate swab.
2. Calgon ringer solution.
3. Bijou tube.
4. Glass beads.
5. Phosphate buffered saline (PBS).
6. Anaerobic cabinet.
7. Vortex machine.
8. Culture media.

A. Mitis-Salivarius Agar (MSA): This agar is a commonly used selective medium for isolating and quantifying *S. mutans* in many cariology clinical and epidemiological studies (**Xiao *et al.*, 2016**).

B. Mannitol salt agar: Is a commonly used selective and differential growth medium in microbiology. It contains a high concentration (about 7.5%-10%) of salt (NaCl), making it selective for Gram-positive *Staphylococcus aureus* and *epidermidis* since this level of salt is inhibitory to most other bacteria (**Bachoon *et al.*, 2008**).

C. Blood agar: is enriched medium used to culture those bacteria or microbes that do not grow easily. Such bacteria are called “fastidious” as they demand a special enriched nutritional environment as compared to the routine bacteria (**Sirois, 2020**).

Other materials:

- 1- Rubber bowl
- 2- Type IV stone
- 3- Gloves
- 4- Masks

5- Plastic petri dish

Procedure

Construction of acrylic samples with different surface texture:

Acrylic samples i.e. tiles of different surface texture will be made. An acrylic sheet of 1 mm thickness will be made using a mold with technique as shown in figure 3.

[figure not shown]

Figure 1: Acrylic samples made from polished and unpolished acrylic sheet.

A half of the sheet will be polished using a conventional polishing technique until a glossy surface appears, whereas, the remaining will be kept without modification. Tiles of 5mm in diameter will be bored using a trephine bur on both sides of the acrylic sheets and each set of tiles i.e. the polished and unpolished samples, will be color coated from its seated surface.

Construction of upper removable orthodontic appliance

An impression will be taken to the maxillary arch using alginate impression material (Hydrogum 5, Zhermack, Badia Polesine, Italy). The negative replica is then poured using type IV stone to make a study model. Four metal discs (5mm in diameter and 1.2mm thickness) will be placed on both sides of the palate as seen in figure 2; A.

[figure not shown]

Figure 2: Construction of the acrylic based orthodontic appliance. A, Study model with acrylic tiles; B, Fitting surface of the acrylic removable appliance.

The wire framework of the removable appliance will be fabricated using a 0.7 mm in diameter stainless steel wire (Spring hard, Dentarum, Ispringen, Germany) to make Adam's clasps on upper first premolars and molars to retain the appliance.

After applying a separating medium, an acrylic base will be fabricated using the orthodontic acrylic powder and liquid (Orthocryle, Dentaurum, Ispringen, German) with a ratio of (2.5 parts powder to 1 part liquid) according to the manufacturer's instruction. Before setting, a sprue or chimney like structure will be created through the acrylic dough to facilitate the metal discs and acrylic sample removal. The appliance then will be removed and the metal tiles will be dislodged using metal pin (Figure 2; B).

The acrylic tiles (5mm in diameter and 1mm thickness) will be placed and fixed into the holes, created by the metal discs, using sticky wax. The acrylic samples will be randomly seated as shown in figure 3.

The appliance will be sterilized using proper sterilization protocol.

Figure 3: The acrylic base containing the acrylic samples.

Method for biofilm detection

The removable appliance will be assigned randomly and blindly and fitted into the oral cavity of the patient for one week. Each individual will be given a pack containing the cleansing pack and an instruction sheet with a web link describing the cleaning regimen for his/ her appliance. The packs are similar in shape and color and will be prepared by a third person who does not know the purpose of the study. The volunteer will be grouped into three groups:

Group 1: patients will be instructed to brush both sides of the removable appliance once a day for 1 minute before bedtime using the toothbrush and the CHX toothpaste provided and water (**Albanna *et al.*, 2017**).

Group 2: patients will be instructed to immerse the appliance in 150 ml cup with tap water and dissolve one cleansing (**Albanna *et al.*, 2017**) tablet for 20 minutes according to the manufacture instructions.

Group 3: Combination of the chemical and mechanical methods first submitted to the mechanical method, followed by the chemical method (**Oliveira *et al.*, 2009**).

At the end of the study period, the acrylic samples will be removed carefully and applied into a petri dish containing PBS via a sterile tweezer. The samples will be then immersed twice in a 25ml sterile tubes containing

PBS to remove the planktonic bacteria and inserted into 5ml bijou tube containing 1mm PBS and 5 sterile glass beads. The sample will be vortex-mixed for 1 min to disseminate the biofilm and create a homogenous solution. Ten-fold serial dilutions will be carried out in PBS before the samples are plated onto blood agar (BA), to give the total anaerobic count, mitis salivarius agar (MS), a selective agar for streptococci and Mannitol salt agar (MA) for Staphylococci spp. BA and MS plates will be incubated anaerobically for 2-4 days at 37°C using anaerobic cabinet whereas the MA will be incubated for 2 days in aerobic condition. All organisms from both selective and nonselective agars will be distinguished by colony morphology and will be characterized by Gram reaction (**Al Groosh *et al.*, 2011**) and other confirmatory tests.

Confirmatory test

1. Catalase testing: Catalase is a common enzyme found in nearly all living organisms exposed to oxygen (such as bacteria, plants, and animals) (**Chelikani *et al.*, 2004**). This test demonstrates the presence of catalase, an enzyme that catalysis the release of oxygen from hydrogen peroxide (H₂O₂). The catalase test is mainly used to differentiate between Gram-positive cocci: members of the genus Staphylococcus are catalase-positive, and members of the genera Streptococcus and Enterococcus are catalase-negative (**Whittenbury, 1964**).
2. Coagulase testing: Coagulase is a protein enzyme produced by several microorganisms that enables the conversion of fibrinogen to fibrin. In the research laboratory, it is used to differentiate between different types of Staphylococcus isolates. Importantly, *S. aureus* is generally coagulase-positive (**Ryan and Ray, 2004**).

Statistical analysis

All the data of the tested samples will be collected and analyzed using SPSS (statistical package of social sciences). In this study the following statistics will be used:

Descriptive statistics

- Mean.
- Standard deviation (SD).
- Minimum and maximum values.
- Statistical tables, figures and charts.

Normality test

Data distribution will be tested first using Shapiro-Wilk test to find that whether our collecting data are normally distributed or not.

Inferential statistics

- ANOVA (if the data parametric) or Kruskal Wallis test (if none parametric) to compare the effect of each cleaning agents on biofilm reduction of removable orthodontic appliance and Tukey HSD pot hoc test if there is significant difference between them.
- Independent t-test (if the data parametric) or Mann Whitney test (if none parametric) to compare the effect of each cleaning agents on biofilm reduction on polished and unpolished surface

In the statistical evaluation, the following levels of significance will be used:

Non-significant NS $P > 0.05$

Significant S $0.05 \geq P > 0.01$

Highly significant HS $P \leq 0.01$

Time table:

Duty	Expected time
Patient Identification and allocation	4 months
Intervention period	3 months
Data collection and analysis	2 months
Writing up the thesis	10 months (starting from the beginning of the study)
Total expected time to finish	About 10 to 11 months

Budget and Funding: The study is self-funded

Dissemination: Master Thesis.

References

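### Only Groups 1 and 3 take home chlorhexidine toothpaste, and the protocol as described neither bars nor records its use on the teeth, so their comparisons with Group 2 could be biased

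*Combined protocol and SAP*

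**What the plan says.** The Exclusion criteria rule out any "Participant taking steroid-based or antibacterial mouthwash or broad-spectrum antibiotics". This is the only control on oral antibacterials that the protocol states.

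Under Method for biofilm detection, the regimens are:

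- **Group 1** brushes both faces of the appliance "once a day for 1 minute before bedtime using the toothbrush and the CHX toothpaste provided".
- **Group 2:** "patients will be instructed to immerse the appliance in 150 ml cup with tap water", with one cleansing tablet dissolved in it. No paste or brush is mentioned.
- **Group 3** is described as "Combination of the chemical and mechanical methods first submitted to the mechanical method, followed by the chemical method". The list of materials for the cleaning regimes confirms that this arm also has the paste: "Combination of brushing with CHX toothpaste and cleaning tablet".

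The same list describes the mechanical kit as "Brush (dental or denture brush) with chlorhexidine (CHX) toothpaste", so the brush may be an ordinary toothbrush; the Group 1 text calls it one.

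Each patient receives a pack, an instruction sheet and a web link, described as covering the cleaning regimen for the appliance. What patients use on their own teeth is not mentioned for any arm.

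After one week of wear, the acrylic tiles are removed and bacteria from them are cultured. The procedure takes no saliva, mucosal or tooth sample. Inferential statistics compares the regimens by ANOVA or Kruskal-Wallis, with Tukey follow-up and no covariate.

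**The concern.** The research question is which method best cleans the appliance. Tile counts depend on how well the appliance is cleaned and, plausibly, on how many bacteria the mouth supplies to it. An antibacterial paste used on the teeth could act through the second route without cleaning the appliance at all.

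The paste is supplied by arm. Randomisation balances what patients bring into the trial, but not a product that only two arms are handed. A patient given a toothbrush and toothpaste for bedtime could easily use them on the teeth as well. Any resulting bias would favour Groups 1 and 3 over Group 2. That bears directly on the mechanical-versus-chemical contrast in the first aim. Nothing measured would separate a cleaner appliance from a less heavily colonised mouth.

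**Working it through.** **1. Arms side by side, from the protocol**

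| | CHX paste and brush supplied | Tablet supplied | Own-tooth toothpaste stated | Use on teeth recorded |
|---|---|---|---|---|
| Group 1 | yes | no | no | no |
| Group 2 | no | yes | no | no |
| Group 3 | yes | yes | no | no |

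Use of the supplied paste on the teeth is possible only in Groups 1 and 3. It can therefore enter the contrasts 1 versus 2 and 3 versus 2. It largely cancels in 1 versus 3, where both arms have the paste. It also largely cancels between polished and unpolished tiles carried in the same mouth.

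**2. The plan's own figure**

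The sample size is 13 per group, so 3 × 13 = 39 patients. It rests on a citation; no effect size, SD or power is given, so it cannot be reproduced. Solving backwards at two-sided 0.05 (sidedness is my assumption), 13 per group gives 80% power for a pairwise difference of about 1.10 SD by the normal approximation, or 1.15 SD by the exact t calculation.

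**3. Shift in an arm mean**

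The documents give no values for uptake or effect, so these are assumptions: a share u of 25–50% of CHX-arm patients also use the paste on their teeth, and this lowers their tile counts by d = 0.5 log10.

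Shift = u × d:
- 0.25 × 0.5 = 0.125 log10 (0.13)
- 0.50 × 0.5 = 0.25 log10

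**4. Shift in SD units**

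b = shift / SD. The SD is also assumed:
- SD 1.0 log10: b = 0.125 to 0.25
- SD 0.5 log10: b = 0.25 to 0.5

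**5. Effect on the tests when the cleaning methods truly do not differ**

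With Groups 1 and 3 both shifted by b, the ANOVA noncentrality is 13 × (2/3) × b², on 2 and 36 degrees of freedom. At b = 0.25 this is 0.54; at b = 0.5 it is 2.17. The Tukey column comes from 20,000 simulated trials per value of b.

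| b | ANOVA rejects | Tukey, Group 1 vs 2 |
|---|---|---|
| 0 | 5.0% | 1.9% |
| 0.25 | 8.9% | 4.4% |
| 0.5 | 22.5% | 13.5% |

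The model uses normal data on a log10 scale and applies the average shift to everyone in the arm. A real mix of users and non-users would also widen the spread. The percentages are illustrations, not estimates.

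**The case against.** The strongest reply is that the protocol already assigns the paste to the appliance. Group 1 is told to brush the appliance with it, and the materials list places it among the cleaning-regime supplies. That is correct. A reader might infer that the paste is handed out with no direction on use, and the text does not support that. What is missing is narrower: a stated bar on other use, a common product for the teeth, and a record. The unseen instruction sheet might supply some of this; if it does, the protocol should say so.

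A second reply is that CHX is part of the tested regimen. This stands for CHX carried back into the mouth on a brushed appliance. It does not stand for brushing the teeth, which is not a way of cleaning the appliance.

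Third, uptake and effect are assumed, and the result is modest. At an SD of 1.0 log10 the ANOVA rejection rate is at most 8.9% against 5.0%; reaching 22.5% needs the upper uptake and an SD of 0.5 log10. This also stands.

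A reader might go further and argue that the exclusion covers only current use, and that the Time table gives 4 months to "Patient Identification and allocation" and 3 months to the intervention, so entry status could be stale at fitting and bias the comparison. The documents do not support this. The Time table lists durations only; it does not say when eligibility is checked or that it is never rechecked. Antibacterial use before entry is not arm-specific, so randomisation balances it in expectation and it adds noise. One patient in 13 with a count suppressed by 2–3 log10 (assumed) would move an arm mean by 2/13 = 0.15 to 3/13 = 0.23 log10, which is ordinary chance imbalance at this size.

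**Conclusion.** The concern holds as a possible, arm-specific bias in Group 1 versus 2 and Group 3 versus 2. It rests on three features of the text: the CHX paste goes to two arms only; own-tooth use is neither standardised nor recorded in the protocol as described; and the outcome is an unadjusted count on tiles worn in the mouth. Its size cannot be derived from the documents. Under the assumed uptake and effect it is 0.13–0.25 log10, or 0.13–0.5 SD across assumed SDs of 0.5–1.0 log10, against the 1.1 SD or so that the trial can detect with 80% power.

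It would be wrong to infer that the bias has been shown to occur, or that the whole trial is affected. Group 1 versus 3 and the polished-versus-unpolished comparison are largely untouched. The change is still worth making before the trial starts, because tooth brushing that was not recorded during the wear week cannot be reliably recovered later.

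**What to change.** - Give all three groups the same non-antibacterial toothpaste, with a separate brush, for their own teeth.
- Label the CHX paste and its brush 'appliance only' on the pack and instruction sheet, and state this in the protocol.
- At the end of the week, ask every patient whether the CHX paste was used on the teeth, and whether any other oral antibacterial or antibiotic was used.
- Keep all randomised patients in the main comparison and add a sensitivity analysis without those who report such use. Treat it as supportive only: the exclusions follow randomisation, and use of the supplied paste on the teeth can arise only in Groups 1 and 3.

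The cost is 39 tubes and brushes, a label, a line on the instruction sheet and one question at the final visit.

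### Tiles are recovered and diluted in plain PBS with no neutraliser or carry-over control, so retained chlorhexidine could lower culture counts in Groups 1 and 3 and be read as better cleaning

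*Combined protocol and SAP*

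**What the plan says.** The section Method for biofilm detection describes the laboratory chain from appliance to plate. At the end of wear, "the acrylic samples will be removed carefully and applied into a petri dish containing PBS". Two rinses in separate tubes follow. The fluid, the purpose of the rinses and the recovery step are given as "PBS to remove the planktonic bacteria and inserted into 5ml bijou tube containing 1mm PBS and 5 sterile glass beads". The tube is vortexed for 1 minute, and then "Ten-fold serial dilutions will be carried out in PBS before the samples are plated onto blood agar (BA"), mitis salivarius agar and mannitol salt agar. The recovery volume is printed as 1 mm; I read it as 1 ml.

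The only purpose given for the rinses is removal of planktonic bacteria. Neither the procedure nor the materials lists mention a neutraliser, a neutralising medium, a carry-over control or a recovery check. Calgon ringer solution is listed among the microbiology materials, but no described step uses it and it is not called a neutraliser.

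The cleaning agents differ by arm:

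- Group 1 brushes "once a day for 1 minute before bedtime using the toothbrush and the CHX toothpaste provided and water".
- Group 2 soaks the appliance in a 150 ml cup with one cleansing "tablet for 20 minutes according to the manufacture instructions".
- Group 3 receives both ("Combination of brushing with CHX toothpaste and cleaning tablet" in the materials list), with the appliance "first submitted to the mechanical method, followed by the chemical method".

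The tablet's ingredients, the paste's chlorhexidine concentration and the interval between last cleaning and sampling are not stated.

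**The concern.** A culture count measures cells that survive and grow after processing. PBS dilutes an antimicrobial but is not described as inactivating one. If agent is still on the tile, or in the biofilm on it, when the beads break the biofilm up, it can go on acting in the tube and on the first plates. The resulting loss of colonies happens in the laboratory, but the analysis would attribute it to cleaning in the mouth.

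Because exposure is set by the assigned regimen, any such loss is tied to treatment. Randomisation and blinding do not remove it, and no second biofilm measure is planned that could expose it. The comparison at stake is the one the research question asks about, namely which method cleans best. Once the samples are plated, carry-over and cleaning can no longer be separated.

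**Working it through.** **The plan's own figure.** The only design figure is 13 patients per group, supported by a citation with no effect size, SD or power, so it cannot be reproduced. Back-solving with the normal approximation (two-sided 0.05, 80% power), 13 per group detects (1.960 + 0.842) × √(2/13) = 1.10 SD between two groups. The point does not depend on this number; it only gives a scale.

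**1. Which arms carry which agent.**

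| Group | Chlorhexidine paste | Tablet |
|---|---|---|
| 1 | yes | no |
| 2 | no | yes |
| 3 | yes, first | yes, afterwards |

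**2. Loosely held residue.** The tile is 5 mm in diameter and 1 mm thick, so one face is π × 2.5² = 19.6 mm² (0.196 cm²) and the whole surface is 2 × 19.6 + π × 5 × 1 = 55.0 mm² (0.550 cm²). Assume a retained film 0.05 to 0.5 mm thick, which gives a volume v of about 1 to 27 microlitres. With complete mixing, two rinses of volume V and recovery in 1 ml leave this fraction of the starting concentration:

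(v/(V+v))² × v/(1+v), with v and V in ml.

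- V = 25 ml (tubes full): 1.5 × 10⁻¹² to 3.2 × 10⁻⁸.
- V = 5 ml (assumed partial fill): 3.8 × 10⁻¹¹ to 8.0 × 10⁻⁷.

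The petri dish step is left out because its volume is not given; it would lower these figures further. Freely soluble residue is therefore not the problem.

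**3. Residue retained on acrylic or in biofilm.** The documents give no loading, so it is assumed. If all of it is released into 1 ml, concentration = loading × area:

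| Assumed loading (microgram/cm²) | In the tube, one face to whole tile (microgram/ml) |
|---|---|
| 0 | 0 |
| 0.1 | 0.02 to 0.055 |
| 1 | 0.20 to 0.55 |
| 10 | 2.0 to 5.5 |

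Each dilution step divides these by ten. Any effect would therefore arise during vortexing and on undiluted or low-dilution plates, which matter most for the cleanest tiles and the sparsest organisms.

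**4. Effect on a count.** If a fraction f of recoverable cells is suppressed on the counted plate, the count falls by −log10(1 − f): f = 0 gives 0; 0.2 gives 0.10; 0.5 gives 0.30; 0.9 gives 1.0 log10.

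**5. Effect on the planned test.** Suppose true cleaning is equal and an artefact lowers Groups 1 and 3 by s SD relative to Group 2. For the three-arm ANOVA (2 and 36 df, 5% level) the noncentrality is 13 × (2/3) × s².

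| Assumed s (SD) | Chance of a significant result |
|---|---|
| 0 | 5.0% |
| 0.25 | 8.9% |
| 0.5 | 22.5% |
| 0.75 | 45.9% |
| 1.0 | 71.6% |

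The values of s, like those of f, are assumptions. They show what the test would do with an artefact of that size, not that one exists.

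**The case against.** The strongest reply is that carry-over may be nil:

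- **Rinsing.** Step 2 shows that free residue is diluted almost completely, provided mixing is complete. This stands, and it narrows the point to retained agent.
- **Retention is not documented.** Nothing in the plan says that chlorhexidine stays on acrylic or in biofilm, or that beads release it. This also stands. Retention is a possibility that the plan neither excludes nor tests.
- **Timing.** Group 1 brushes at bedtime, so a daytime sampling visit would leave hours of wear in between. That lowers the risk, but the interval is not fixed and no time of day is given for Groups 2 and 3.
- **Countable dilution.** A week of oral biofilm may be counted at high dilutions, where any effect shrinks. The plan gives neither expected counts nor a countable dilution, so this is open.

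Two stronger readings are tempting and should not be made. A reader might infer that the combined arm is favoured because it carries both residues. But in Group 3 the soak follows the brushing and could wash chlorhexidine off, leaving less than in Group 1; the documents do not settle which. A reader might also infer that the tablet leaves an active residue. Its ingredients are not given and a soluble residue would mostly rinse away, so that part is weaker.

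**Conclusion.** The omission is certain on the text: every fluid from dish to dilution series is PBS, no control for carry-over is described, and the agents differ by arm. The consequence is possible but not shown. Its size cannot be derived from the documents and may be zero, and its direction for the combined arm is undetermined. The contrast most exposed is Groups 1 and 3 (chlorhexidine) against Group 2.

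The 0.10 to 1.0 log10 losses and the 8.9% to 71.6% rejection rates rest wholly on assumed suppression and artefact sizes and must not be read as estimates. The point is worth acting on because the safeguard is cheap and cannot be added once samples are plated. It gives no ground for saying that the planned counts will be biased.

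**What to change.** 1. Replace PBS in the bijou tube and the first dilution with one neutralising diluent, identical in all three arms. It should be active against chlorhexidine and, once the tablet's active agent has been confirmed from its label, against that agent too. No recipe should be fixed before then.
2. Before the first patient, treat spare unworn tiles with each regimen, add a known inoculum, and confirm that recovery matches that from untreated tiles. Confirm also that the diluent itself does not alter recovery. State the acceptable difference in log10 beforehand. Running plain PBS alongside would show whether there was anything to neutralise. Unworn tiles carry no oral biofilm, so this checks retention on acrylic only.
3. Record for each patient the interval from last cleaning to sampling and report it by arm.

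The cost is a different diluent, one short bench check on spare tiles and one extra data item. Nothing changes for patients, allocation, sample size or the planned tests.
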